For patients assigned to the “Fast Track” arm, the Fast Track clinic supervisor will schedule an appointment for the patient with an ACP. For patients assigned to the standard treatment arm, the booking clerk will schedule an appointment for the patient with a sleep physician. Patients will be asked to arrive 15 - 20 minutes prior to the appointment to complete study questionnaires. The booking clerks will notify the RA of the initial appointment date and time.

STUDY PROCEDURE

BASELINE VISIT & TREATMENT PLAN

When patient arrives, the RA will ask the patients to complete the following questionnaires (ESS, Short SAQLI without treatment section, and HUI). The study will require an ESS at the time of the baseline visit, even though there may be multiple ESS questionnaires in the patient's chart.

If required, the sleep physician will order a polysomnography (PSG). The RA will check that the PSG is ordered as "urgent". The following will be collected: PSG date, AHI, mean oxygen saturation and percentage of time under 90%.

The RA will access the CPAP database to retrieve the patient's treatment type. The RA will retrieve the patient's treatment start date for the following treatments by:

- CPAP/BAP – retrieving and calling the homecare company OR CPAP database,
- Oxygen only – looking at the patient's chart for the date when the patient was contacted about the PSG results (if the patient is previously on oxygen) OR determining when the patient started on oxygen,
- Dental appliance – calling the dentist,
- Weight loss – looking in the patient's chart for the date treatment options were offered

Possible scenarios	Action
Patient cancels or does not show to the appointment	The RA will note the original appointment date and the rescheduled date.
Patient does not show for 3 or more appointments	Patient is discharged from the CPAP clinic and the study.
Patient stops their initial treatment	The RA will note new treatment. 3-month and 1-year appointments will still be based on the original treatment date.
Multiple patients need to meet the RA at the same time (recruitment, clinical visits)	Possible options: 
 1) Ask an another RA to assist in one of the appointments 2) Ask The Fast Track clinic supervisor to obtain clinical study data at visit

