The RA will create a list (every 3 months) of patients who have completed their 3-month follow-up appointment for the booking clerk. The booking clerk will create a tracking task in the scheduling system to book the appointment several months before the 1-year target date. When the appointment is book, booking clerk will notify RA of appointment date and time. Upon receiving the appointment date, RA will complete a HSAT requisition for the booking clerk to book patient for a HSAT (in-house or with the patient's CPAP company) on the day of the follow-up appointment or whenever is most convenient for the patient. HSAT test is to be completed with a Remmers recorder.

The RA will attempt to call all three month and one year patients who do not have a follow up appointment booked through the Sleep Centre to coordinate the best date and time to complete the questionnaires.

If the patient does not have a follow-up appointment booked at the Sleep Centre. We will use the date that the patient returns their questionnaire as the final appointment date; however, the research associate should note that it is the follow-up date not the final appointment date.

At Time of Appointment

The RA will give the patient a questionnaire package (ESS, Short SAQLI including treatment section, HUI, VSQ-9) at the time of visit. The ESS, Short SAQLI including treatment section and the HUI surveys are to be completed before the patient enters the clinical appointment. The VSQ9 survey is

to be completed after the patient completes their clinical appointment. Download data will be obtained by the Fast Track clinic supervisor or by the therapist. The patient will not be compensated for parking if the follow-up visit is part of the patient's clinical care.

If there are any information missing from the Fast Track Summary sheet (i.e. Triaging criteria, co-morbidities or medication), the RA will retrieve them from the chart or from the CPAP database before/during the time of visit.

Possible scenarios	Action

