	Partial pressure of CO2 on ABG	Netcare – will need to ask a person with access to Netcare (The Fast Track clinic supervisor or [name])	Photocopy
	HSAT Date	Chart	Handwritten
Baseline Visit	Initial baseline visit date	Sleep clinic's CIS system.	Handwritten
	Actual baseline visit date		
	ESS	At baseline visit.	Original
	Health Utilities Index		
	Short SAQLI (without treatment section)		
	Current medications	Patient's chart: 1) Patient info sheet (yellow) when patient comes in for the HSAT, 2) Physician's initial visit letter 3) Patient's self-filled questionnaire, 4) Administrative data from AHS	Handwritten
	Comorbidities		
	PSG date (if applicable)	Sleep clinic's CIS system.	Handwritten
	PSG - AHI, mean O2 saturation, time under 90%	Patient's chart - PSG report	Handwritten
	Treatment start date	CPAP database, homecare company (CPAP/BAP), patient's chart (Oxygen), dentist (dental appliance)	Handwritten
	Treatment type	CPAP database	Handwritten

	Data to collect	Data source	Photocopy, handwritten or original copy
3-Month/1-Year Follow-up	Initial 3-month/1-year visit date	Sleep clinic's CIS system. At 3-month and 1-year visit.	Handwritten
	Actual 3-month/1-year visit date		
	ESS		Original copy
	Health Utilities Index		
	Short SAQLI (with treatment section)		
	Positive airway pressure adherence (1 month directly prior to the appointment) & date		Photocopy
1-Year only	Healthcare utilization - cumulative sum of outpatient physician visits, hospitalizations and length of stay, and urgent care/emergency room visits	DIMR Database	Electronic copy
	Healthcare utilization – additional physician consultation time	Patient's chart: Written communication between ACPs and physicians are recorded on a yellow sheet.	Photocopy
	Healthcare costs – costs for sleep physician and ACP visit, diagnostic sleep testing costs for HSAT and PSG	Taken from the Alberta Health Schedule of Medical Benefits, Health Sciences Association of Alberta (HSAA) Collective Agreement and the FMC sleep Sleep Centre Medical Director	Electronic copy
	Healthcare costs – CPAP therapy costs	Current market pricing through respiratory homecare providers	Electronic copy
	Healthcare costs – hospitalization costs	DIMR and AHS Finance department	Electronic copy
	Healthcare costs – costs for ambulatory visits	Canadian Institute for Health Information (CIHI) and DIMR	Electronic copy

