Evaluation of a “Fast Track” Respiratory Therapy Clinic for Patients with Suspected Severe Sleep-Disordered Breathing

STATISTICAL ANALYSIS PLAN

NCT#: 02191085

Document Date: February 16, 2017

Evaluation of a "Fast Track" Respiratory Therapy Clinic for Patients With Suspected Severe Sleep-Disordered Breathing

Statistical Analysis

This study will use a modified intention to treat analysis, in which results will be analyzed for patients who are randomized and have treatment adherence data three months after initiating PAP therapy.

Paired t tests will be used to compare clinical outcomes from baseline to 3 months and one year and unpaired t tests will be used to compare time to treatment initiation and measures of patient demand. Multiple logistic regression will be used to identify predictors of study outcomes using variables identified as predictive on univariate regression. Outcomes will be transformed into binary variables based on clinically relevant cut-offs.

The economic analysis will be performed using the perspective of a publicly funded healthcare system. An estimate of mean utility scores based on the HUI questionnaire will be calculated and the average quality-adjusted life- year (QALY) will be calculated for each study arm. Using bootstrapping, we will compare the difference in mean costs and QALYs between the study arms to generate an incremental cost-effectiveness ratio for an ACP-led clinic compared to traditional physician-led care. Sensitivity analyses will be performed to evaluate the effect of changes in physician fees, RT salaries, diagnostic testing costs and treatment costs.

All study outcomes will be analyzed in different subgroups to clarify the impact of ACP-led care for patients with different patient flow pathways or clinical treatments. Pre-specified subgroups include:

- Patients who undergo PSG vs. patients who do not undergo PSG
- Patients treated with bilevel PAP vs. patients treated with CPAP
- Patients who are treated with oxygen vs. patients treated without oxygen

Sample Size

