The study is powered to assess the non-inferiority of ACP-led care compared to usual care by sleep physicians. A non-inferiority margin of -1 hour of PAP adherence was determined by consensus of the investigators and has been used in previous studies comparing different models of care for SDB. One hundred thirty eight patients (69 in each arm) will be required to achieve 90% power with a type I error of 0.05, using this non-inferiority margin and a standard deviation of 2 hours of nightly CPAP use. The standard deviation used in the sample size calculation was based upon the results of two previous studies. To account for withdrawals and loss to follow-up (approximately 15% at the FMC Sleep Centre), recruitment will continue until three-month adherence data is available for 150 patients.

Reference: Ip-Buting A, Kelly J, Santana MJ, Penz ED, Flemons WW, Tsai WH, et al.

Evaluation of an alternative care provider clinic for severe sleep-disordered breathing: a study protocol for a randomised controlled trial. *BMJ Open*. 2017 Mar;7(3):e014012.

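### The SAP names no between-arm test or confidence interval for the powered PAP-adherence comparison or for the clinical outcomes that it assigns to paired t tests

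*SAP*

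**What the plan says.** The Statistical Analysis section of the SAP assigns methods by type of outcome.

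- **Clinical outcomes:** "Paired t tests will be used to compare clinical outcomes from baseline to 3 months and one year". The section does not list these outcomes.
- **Two-sample tests:** "unpaired t tests will be used to compare time to treatment initiation and measures of patient demand".
- **Regression:** multiple logistic regression is to look for predictors of outcomes that have been made binary. Candidate variables come from univariate screening, and study arm is not named as a term.
- **Economic analysis:** by bootstrapping, "we will compare the difference in mean costs and QALYs between the study arms".
- **Subgroups:** "All study outcomes will be analyzed in different subgroups to clarify the impact of ACP-led care". No method is named.

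The Sample Size section adds: "The study is powered to assess the non-inferiority of ACP-led care compared to usual care by sleep physicians". It gives a margin of -1 h of PAP adherence, an SD of 2 h, a type I error of 0.05, 90% power and 69 patients per arm. It names no test, confidence interval or sidedness.

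The protocol has no statistical section, but it shows what is measured and when.

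- **Baseline visit:** "the RA will ask the patients to complete the following questionnaires (ESS, Short SAQLI without treatment section, and HUI").
- **3 months and 1 year:** "The RA will give the patient a questionnaire package (ESS, Short SAQLI including treatment section, HUI, VSQ-9) at the time of visit".
- **PAP use:** in the Summary Sheet table it appears only under follow-up, as "Positive airway pressure adherence (1 month directly prior to the appointment) & date".
- **HSAT:** done at recruitment and ordered again for both follow-ups.

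**The concern.** Patients are randomised so that ACP-led care can be compared with physician-led care. A paired t test asks a different question: did patients change over time? Run within each arm, it gives two separate before-and-after results. Run on all patients together, it leaves study arm out altogether. Eligible patients are previously untreated and have severe disease, so improvement in both arms would be no surprise. It would not show whether one model of care did worse.

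The sentence separates paired from unpaired tests and puts clinical outcomes in the paired group. By inference from the visit schedule, that group includes ESS, SAQLI and HUI, and possibly the repeated HSAT measures.

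The gap matters most for the powered outcome. PAP hours cannot fall under the paired-test sentence, because it has no baseline value. It is also not among the outcomes given unpaired tests. The hypothesis that fixed the number of patients therefore has a margin but no written analysis or decision rule. Test, interval and level would be open to choice once the data are in hand.

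**Working it through.** **1. Which outcome has a stated between-arm method?**

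| Outcome | Baseline value | Follow-up value | Between-arm method stated |
|---|---|---|---|
| PAP hours (powered) | no | yes | none |
| ESS, SAQLI | yes | yes | none (paired test only, by inference) |
| HUI | yes | yes | only indirectly, through bootstrapped QALYs |
| HSAT measures | yes | yes | none (possibly the paired test) |
| VSQ-9 | no | yes | none |
| Time to treatment, patient demand | – | – | unpaired t test |
| Costs, QALYs | – | – | bootstrap |

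**2. The SAP's sample size.** Inputs from the Sample Size section: margin 1 h, SD 2 h, power 90%. A true difference of 0 is assumed.

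n per arm = 2 × (z for alpha + z for power)² × SD² / margin²

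- One-sided 5%: 2 × (1.645 + 1.282)² × 4 / 1 = 68.5, so 69 per arm and 138 in total. This matches the SAP.
- One-sided 2.5%: 2 × (1.960 + 1.282)² × 4 / 1 = 84.1, so 85 per arm and 170 in total. This does not match.

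The sample size therefore implies a two-sample comparison at one-sided 5%, equivalent to a two-sided 90% CI. The SAP does not say so.

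**3. What the choice of level changes.** Assume that the 150 patients with adherence data split into 75 per arm. Then SE = 2 × √(2/75) = 0.3266 h with 148 degrees of freedom. Non-inferiority is concluded if the observed ACP minus physician difference is above:

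- 90% CI rule: -1 + 1.655 × 0.3266 = -0.46 h
- 95% CI rule: -1 + 1.976 × 0.3266 = -0.35 h

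The two rules disagree when the observed difference falls between these limits. The probability is 5.9% if the true difference is 0, at most 12.7% (near -0.41 h), and 2.5% at -1 h.

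| Power (t-based, true difference 0) | 69 per arm | 75 per arm |
|---|---|---|
| one-sided 5% (90% CI) | 89.9% | 92.0% |
| one-sided 2.5% (95% CI) | 83.0% | 86.0% |

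**4. Illustration for ESS-type outcomes.** The documents give no SD for ESS, SAQLI or HUI, so every input here is assumed: 75 complete pairs per arm, SD 1 at both visits, correlation r between visits, and a true improvement of 0.8 SD with physicians and 0.4 SD with ACPs. Tests are two-sided at 5%.

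- Paired test within an arm: SD of change = √(2(1 − r)).
- ANCOVA between arms: SE = √((2/75)(1 − r²)).
- Unpaired test on change: SE = √((2/75) × 2(1 − r)).

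| | r = 0.3 | r = 0.5 | r = 0.7 |
|---|---|---|---|
| Paired tests significant in both arms | 82% | 93% | 99% |
| ANCOVA detects the 0.4 SD shortfall | 72% | 80% | 93% |
| Unpaired test on change detects it | 54% | 68% | 88% |

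The first row and the other two answer different questions. The first shows that both arms can readily be reported as improved although one has half the benefit of the other. A separate simulation with change SD 1 makes the same point. Both paired tests were significant in 100% of runs with equal changes (0.75 and 0.75 SD) and in 99.0% with unequal changes (1.0 and 0.5 SD). The unpaired test on change rejected in 4.8% and 86.4% of those runs.

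**The case against.** The strongest reply is that the intention to compare arms is plain. The Sample Size section states a non-inferiority hypothesis with a margin, the economic analysis compares arms, and the subgroup paragraph is about the effect of ACP-led care on every outcome. That is correct, and it defeats one tempting inference, that the plan abandons the randomised comparison. What is missing is the method, not the aim.

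A reader might also infer that the plan yields no estimate at all of the difference in sleepiness or quality of life. The documents do not support that. The SAP does not say that the arms are pooled, and two within-arm changes can be subtracted. The subtraction comes with no confidence interval or test.

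The logistic regression is a second method for study outcomes, and arm could be entered in it. The SAP does not say that it will be. Univariate screening might not retain it, and a binary outcome cannot test a -1 h difference in mean hours.

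On the level, a non-inferiority test is directional and 69 per arm points to one-sided 5%. A 95% CI would only be stricter. This stands: the level is recoverable, and the disagreement rates measure an ambiguity of wording, not a known error. ANCOVA is also a choice of efficiency. An unpaired test on change would close the gap too, with more variance: ANCOVA has (1 + r)/2 of the change-score variance, or 0.65, 0.75 and 0.85 at the three correlations.

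**Conclusion.** The concern holds. As written, the SAP gives no test or confidence interval for the ACP minus physician difference in PAP hours, ESS, SAQLI, VSQ-9 or the HSAT measures, and reaches HUI only through QALYs. The most serious gap is PAP hours, because it is the powered outcome; the clinical outcomes come next. This must be fixed before analysis.

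For PAP hours the size is limited. The 90% and 95% CI rules disagree in about 6% of trials if care is truly equal and in at most 13%, given an SD of 2 h and an assumed 75 per arm. For the clinical outcomes no size can be given for this trial. The figures in SD units rest on assumed effects and correlations, and it would be wrong to read them as an error rate here. That ESS, SAQLI, HUI and HSAT belong to the paired-test group is itself an inference from the visit schedule.

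**What to change.** 1. **Primary analysis.** State it as the ACP minus physician difference in mean nightly PAP hours at 3 months. Conclude non-inferiority if the lower limit of the two-sided 90% CI (one-sided 5%, the level that the sample size uses) is above -1 h. Fix this one level before analysis. If a 95% CI is preferred, restate power as about 83% at 69 per arm or 86% at 75 per arm.
2. **Clinical outcomes with a baseline.** List them. Compare ESS, SAQLI, HUI and the repeated HSAT measures between arms at 3 months and 1 year by ANCOVA adjusted for the baseline value, with 95% CIs. Score SAQLI on the items collected at both visits, because its treatment section is absent at baseline. Claim no non-inferiority for these outcomes, since no margin is stated.
3. **VSQ-9.** Use an unpaired comparison between arms, as it is collected only at follow-up.
4. **Paired t tests.** Keep them as description of change within each arm.

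The cost is a few sentences of SAP text and slightly more analysis. The baseline values are already collected, and no patients are added.

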Patients with only a verbal consent to the study	The RA will review the study with the patient and obtain a written consent to the patient regardless if the patient is eligible or not. 
If the patient revokes their verbal consent, the RA will remove patient from the study, identify the reason why the patient does not want to participate in the study. Because the patient has not yet had an initial appointment with a physician or an ACP, the patient will not be counted as part of the 150 patients recruited.
 
The RA will notify the Fast Track clinic supervisor of patient.

Patient delays their treatment	If the patient delays their treatment due to insurance purposes, treatment start date will be the date they start their treatment. 
If the patient delays their treatment due to other medical reasons, the treatment start date will be the date that treatment was offered. Three-month and one year follow-up data will be collected as per usual procedures.

Patient has had multiple PSGs after the indicated treatment start date	The RA will pull the file and review with the LSP as the treatment start date may need to be modified.
Patient does not have sleep disordered breathing after further testing (e.g., PSG)	The treatment start date will be the date of the diagnostic test. Three-month and one year follow-up data will be collected as per usual procedures.

3-MONTH & 1-YEAR FOLLOW-UP (\pm 2 WEEKS)

3-Month Appointment Date and Time

The RA will create a list (weekly) of patients who have completed their initial appointment for the booking clerk. The booking clerk will review the scheduling system to book and/or confirm patient's 3-month appointment. Upon receiving the appointment date, the RA will complete a HSAT requisition for the booking clerk to book patient for a HSAT (in-house or with the patient's CPAP company – if ordering a HSAT from the home care provider, state on cover letter to send the raw data to FMC Sleep Centre) on the day of the follow-up appointment or whenever is most convenient for the patient. HSAT test is to be completed with a Remmers recorder. Note: if the patient is on O2, request the HSAT done on room air or without O2. If the HSAT is completed on O2 note make a note that it was completed on O2 on the patients chart.

1-Year Appointment Date and Time

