***Note: All handwritten, photocopied and original information will be transcribed to electronic format by RA and all data will be stored at the W21C.**

APPENDIX 1

"Fast Track" Summary Sheet

Study consent: Yes
 No

Triage Criteria: Level 3 HSAT
 ANC = NC____, HBP____, HSnore____, HApea____

Referral Date: _____

Eligibility process

- Patient >= 18 years old
- Patient does not have a previous treatment of SDB

One of the following:

- RDI >= 30 events/hr
- Mean nocturnal O2 saturation <= 85%
- RDI >= 15 events/hr AND partial pressure of CO2 >= 45 mmHg on ABG

Eligible: Yes: ACP Resp
 No

Baseline visit date: _____

- ESS
- Health Utilities Index
- SAQLI
- Current medications (if any)
- Comorbidities

PSG: Yes, date_____
 No

Current Medications (list):

Comorbidities (list):

 High Blood Pressure	 Heart Failure
 Asthma	 Other Lung Disease
 Diabetes	 Dialysis
 Depression	 Fibromyalgia
 Angia/Heart Attack	 Heart Disease
 COPD/Emphysema	 Stroke
 Kidney Disease	 Atrial Fibrillation/ Arrhythmia
 Psychiatric Disease	

ID#: _____

Treatment date: _____

Initial 3mth Appointment Date: _____

Actual 3mth Appointment Date: _____

Checklist:

- ESS
- Health Utilities Index
- SAQLI
- Positive airway pressure adherence
(1 month)
- Ambulatory sleep test
- CAHPS-GC

Questionnaire Mailing Dates:

- Yes. Mail date_____
- Receive date_____
- No

Initial 1 yr Appointment Date: _____

Actual 1 yr Appointment Date: _____

Checklist:

- ESS
- Health Utilities Index
- SAQLI
- Positive airway pressure adherence
(1 month)
- Ambulatory sleep test
- CAHPS-GC
- Healthcare utilization

Questionnaire Mailing Dates:

- Yes. Mail date_____
- Receive date_____
- No

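### Time to treatment is compared only among patients who started PAP and reached three months, so a difference between arms in never starting can distort the access result in either direction

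*SAP*

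**What the plan says.** The SAP (Statistical Analysis) names one analysis set, a modified intention-to-treat set in which "results will be analyzed for patients who are randomized and have treatment adherence data three months after initiating PAP therapy". Within it, "unpaired t tests will be used to compare time to treatment initiation and measures of patient demand". Neither document gives a time origin for the interval or a rule for a randomised patient with no start date.

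The protocol (Baseline Visit & Treatment Plan) defines the start date case by case. In three situations it records an offer or a test:

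- Treatment put off for medical reasons other than insurance: "the treatment start date will be the date that treatment was offered".
- Weight loss: the date comes from the "chart for the date treatment options were offered".
- No sleep-disordered breathing on further testing: "The treatment start date will be the date of the diagnostic test".

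For an insurance delay, "treatment start date will be the date they start their treatment", so no date exists if treatment never starts. After three or more missed appointments, "Patient is discharged from the CPAP clinic and the study". The scenarios table under Eligibility adds that someone who leaves without a baseline visit is not counted in the study. Because the baseline appointment is booked after allocation, with the provider that the arm dictates, such a patient may already have been randomised.

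The Summary Sheet (Appendix 1) has a field for "Referral Date", and the data table records the HSAT date. Neither has a field for the randomisation date.

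**The concern.** Speed of access is what a clinic called Fast Track is meant to deliver, and this is the outcome that measures it. Membership of the analysis set is decided after randomisation and depends on starting PAP, which is part of what access means. Patients facing a long wait have the most time to give up. Averaging only those who started removes long waits, and removes more of them from the arm that loses more patients. The two averages then describe differently selected groups, and randomisation no longer protects the comparison.

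The assigned dates raise a second problem. If the set is widened to all randomised patients and the recorded start dates are used unchanged, some patients who were only offered treatment, or were found not to need it, would count as having started.

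**Working it through.** **1. The plan's own figure.** The only design calculation concerns adherence (SAP, Sample Size): margin 1 hour, SD 2 hours, 90% power, type I error 0.05. Per arm, n = 2 × 2² × (1.645 + 1.282)² / 1² = 68.5, so 69 per arm and 138 in total. This reproduces the plan at one-sided 0.05. No power, variance or margin is given for time to treatment.

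**2. Who has a usable start time.**

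| Randomised patient | Recorded start | In planned set? | Value if set is widened? |
|---|---|---|---|
| Starts PAP, has three-month data | Actual | Yes | Yes |
| Starts PAP, lost before three months | Actual, if known | No | Yes, if known |
| Insurance delay, never starts | None | No | No |
| Discharged after missed visits, withdrawn or lost before starting | None or unknown | No | No |
| Medical delay | Date offered | Only if PAP data follow | Assigned |
| Weight loss | Date options offered | Only if PAP data follow | Assigned |
| No sleep-disordered breathing | Test date | No | Assigned |

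The set does the first exclusion. The t test prevents repair by changing the set alone.

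**3. Arithmetic with fixed never-start shares.** All inputs are assumed: starters' mean wait m, never-start share p, horizon 365 days. Restricted mean days untreated = (1 − p) × m + p × 365. Differences are standard minus Fast Track, so positive favours Fast Track.

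- Understated. Fast Track m = 60, p = 5%: 57 + 18.25 = 75.25. Standard m = 90, p = 15%: 76.5 + 54.75 = 131.25. Starters only +30; all randomised +56.
- Overstated, with a change of sign. Same waits, shares exchanged: Fast Track 51 + 54.75 = 105.75; standard 85.5 + 18.25 = 103.75. Starters only +30; all randomised −2.
- Benefit hidden. Fast Track m = 95, p = 5%: 90.25 + 18.25 = 108.5. Standard m = 90, p = 15%: 131.25. Starters only −5; all randomised +22.75.
- Equal shares, waits 60 and 90: +30 × 0.95 = +28.5 at 5%, and +30 × 0.85 = +25.5 at 15%. The shift is 1.5 to 4.5 days, with no change of sign.

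Break-even points: in the hidden-benefit case the sign reverses once 90 + 275p exceeds 108.5, that is p above 18.5/275 = 6.7% on standard care. With waits of 60 and 90 and 5% on standard care, it reverses once 60 + 305p exceeds 103.75, that is p above 43.75/305 = 14.3% on Fast Track.

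**4. A model in which waiting itself causes loss.** Assumed: log-normal waits with log-SD 0.7, a constant monthly risk of giving up, and a 180-day horizon with non-starters at 180. Both arms have a median wait of 75 days.

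| Monthly give-up, Fast Track v standard | Never start | Starters-only difference | Untreated-days difference, all randomised |
|---|---|---|---|
| 3% v 10% | 9% v about 25% | about −10 | about +12 |
| 3% v 5% | 9% v 14% | about −3 | about +3.5 |
| equal | equal | 0 | 0 |

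The first row varies by about one day (−9 to −10, +11 to +12), and the larger share between 25% and 26%, according to how the monthly risk is converted to a daily one.

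**5. Unequal waits.** With medians of 45 and 90 days and the same give-up risk in both arms, the mean difference if nobody gave up is (90 − 45) × exp(0.7²/2) = 45 × 1.278 = 57 days. Among starters it is about 54, 49 and 45 days at 2%, 5% and 8% per month. The 180-day restricted difference is about 43 days in each case. It measures a different quantity, so its distance from 57 is neither evidence for the method nor evidence against it.

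**The case against.** The strongest reply is that everyone in the planned set has started PAP, so the t test has a time for each patient and is not itself at fault. That is correct about the order of events: the modified intention-to-treat set removes non-starters before any test is run. It does not rescue the comparison, because the selection follows randomisation and a t test could not use the excluded patients if they were put back.

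Second, a reader might infer that the plan will understate the Fast Track benefit or reverse it. The documents do not support that. The only attrition figure is about 15% for withdrawals and loss to follow-up combined (SAP, Sample Size); it is not split by arm and is not a never-start rate. Overstatement is equally possible.

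Third, a reader might infer that the trial lacks a usable time zero. It does not: referral and HSAT dates are recorded and precede allocation. The gap is that no origin is stated.

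Fourth, a reader might infer that the assigned dates already corrupt the planned analysis. Patients with no sleep-disordered breathing, or with weight loss alone, would normally have no PAP adherence data and so fall outside the set. The medical-delay rule can reach it, if such a patient later uses PAP. The three rules matter mainly once the set is widened.

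Finally, the 180-day outcome should not be presented as closer to the plain mean wait. In the 45 v 90 day example it is further from it (about 43 against 57 days).

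**Conclusion.** The concern holds in a limited form. As written, the access comparison is made in a group selected after randomisation on having started PAP and having three-month data, and the named test has no means of including non-starters. The resulting error depends on how far the never-start shares differ between arms. With equal shares of 5% to 15% it is a few days; with a gap of ten percentage points or more it can reach several weeks or change the sign. These sizes rest wholly on assumed waits, give-up rates and horizons, because the documents supply none, so the direction and size in this trial are unknown. The adherence comparison, on which the trial is powered, and its 138 patients do not depend on this point.

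**What to change.** For this outcome only, change the SAP as follows:

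- **Set.** Analyse all randomised patients in their assigned arm, including those without a baseline visit and those discharged after missed appointments.
- **Origin.** State one that the arm cannot affect: the referral or HSAT date already recorded, or the randomisation date if a field is added.
- **Event.** Use actual treatment start, and say which treatment types count. Keep the three assigned dates for scheduling follow-up only.
- **Estimate.** Show cumulative incidence of treatment start by arm, or compare restricted mean days untreated to a fixed horizon such as 180 days, with known non-starters at the horizon.
- **Incomplete cases.** Censor patients whose start status is unknown instead of scoring them at the horizon. Treat a finding of no sleep-disordered breathing as a competing end.

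The cost is SAP wording, a change to the protocol's rules on who is counted, and at most one extra date field. A capped restricted mean is a different quantity from the plain mean wait, and reports should say so. Little or no power should be lost: in simulations with 88 per arm, assumed medians of 60 and 78 days and every start status known, the starters-only t test and a t test on capped days both had about 53% power.
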